3.1 Research Design

This is a prospective, phase II, single-centre, single-blind, cross-over, randomized negative-controlled (without microneedle (MN)) trial at Hospital Canselor Tuanku Muhriz (HCTM), Universiti Kebangsaan Malaysia. Eligible participants will be randomized in a cross-over fashion to one of 24 treatment sequences as shown in **Figure 4**.

This crossover design is chosen over the more conventional parallel-group randomized trial since the lesser intra-patient variability than the inter-patient variability, thus minimising the required sample size. The study investigators also do not anticipate the inherent disadvantages associated with this trial design (greater attrition rate, prolonged carry-over effects and the inconsistency of participant's condition) will be present in this study.

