3.8 Randomization procedure

For random allocation, simple randomization with random allocation rule (RAR) will be used by which a list of random numbers will be generated in a balanced 1:1 ratio (based on 24 different treatment sequences) using the randomizeR package version 20.0 executed on R platform.³⁴ The list of generated random numbers will be used to allocate the study participants to either intervention or control branch. The allocation sequence generated will be kept in a password-protected document that is only accessible to the statistician to maintain allocation concealment. To further guarantee allocation concealment is satisfactory, randomisation code will not be revealed until the participants have been definitively recruited into the trial, which is after all baseline measurements are made and all eligibility criteria are deemed fulfilled. Besides, allocation concealment is further assured by ensuring the information on the intervention allocation is only given to the person who will be administering the allocation via secured phone calls (central randomization). Consecutive recruitments will be made until the final intended sample size is reached.

For this study, the study participants, outcome assessors, care providers and data handlers will be blinded to the study interventions. Only the statistician and the person who will be administering the interventions will be unblinded to the study interventions. Besides, unique code to indicate each treatment sequence assignment will be utilised to ensure that the unintentional / intentional unblinding of one trial participant will not compromise the integrity of blinding for the rest of study participants. The main unblinded trial persons (the statistician and the key person who will be administering the intervention) are instructed not to divulge the identity of the allotted treatments to other blinded trial persons. The success of blinding will be determined by asking the blinded trial persons (e.g. study participants, care providers, outcome assessors) to guess the interventions received and then compare the results obtained with what would be anticipated by chance. Blinding indices such as James' Blinding Index or Bang's blinding Index could also be computed to objectively evaluate the success of blinding.^{35,36}

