The investigator identified and drew a grid of 1cm × 1cm at the dorsum hand, which served as an ideal site for cannulation. The administrator of intervention (procedurist) will apply either 1 FTU of EMLA Cream (approximately 0.68 g/cm²) or 0.5 FTU (approximately 0.369 g/cm²) over the preparation area. If the patient is subjected to MN patching at his/her visit, the MN patch will be applied by thumb force and pressed firmly against the hand surface for 5 seconds to patch MN to the skin entirely before applying EMLA cream. Otherwise, an empty (i.e. without MN) PVA-containing PET sham patch will be applied instead. Besides, the height-to-base ratio (4:1) used for MN will also optimally minimise its adverse effects (pain, redness), thus preserving the masking (blinding) of study participants from knowing the types of interventions received. The preparation area will be covered with an adhesive dressing (Tegaderm™; 3M, Maplewood, Minnesota, USA) after EMLA cream application. After the allocated application time (15 or 30 minutes), the attending medical officer will set up the transfusion line with a 22-gauge hypodermic needle inserted into the dorsum hand. Throughout the process, the parents/guardians will be allowed to stay by the patient's side at all times.

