3.15 Study flow

[figure not shown]

Figure 4. The flowchart of this randomized crossover trial showing 4 random intervention sequences out of 24 permutations generated. Intervention A: MN + 1 FTU EMLA 30 minutes application; Intervention B: MN + 0.5 FTU EMLA 30 minutes application; Intervention C: MN + 1 FTU EMLA 15 minutes application; Intervention D: 1 FTU EMLA Only 30 minutes (controls)

| | | | |
|------|------|------|------|
| ABCD | BACD | CADB | DABC |
| ACBD | BADC | CABD | DACB |
| ABDC | BDAC | CBAD | DBAC |
| ACDB | BDCA | CBDA | DBCA |
| ADBC | BCAD | CDAB | DCAB |
| ADCB | BCDA | CDBA | DCBA |

Table 1. The exhaustive list of permutations of intervention sequences that will be randomized to the participants of this trial. Intervention A: MN + 1 FTU EMLA 30 minutes application; Intervention B: MN + 0.5 FTU EMLA 30 minutes application; Intervention C: MN + 1 FTU EMLA 15 minutes application; Intervention D: 1 FTU EMLA Only 30 minutes (controls)

[figure not shown]

Figure 5. Schematic flow of the clinical trial.

GANTT CHART

| Project Activities | Timeline of event | | | | | | | | | | | | | | |
|---------------------------------------|-------------------|---|---|---|---|---|---|---|----|----|----|---|------|---|---|
| | 2021 | | | | | | | | | | | | 2022 | | |
| | 2 | 3 | 4 | 5 | 6 | 7 | 8 | 9 | 10 | 11 | 12 | 1 | 2 | 3 | |
| Proposal preparation | ● | ● | ● | ● | ● | | | | | | | | | | |
| Ethics approval | | | | | ● | ● | | | | | | | | | |
| Microneedle fabrication | | | | | ● | ● | ● | | | | | | | | |
| Purchasing of PainMonitor | | | | | ● | ● | ● | | | | | | | | |
| Patients' recruitment | | | | | | ● | ● | ● | | | | | | | |
| Launching of clinical trial | | | | | | ● | ● | ● | ● | ● | ● | ● | ● | ● | ● |
| Data analysis and interpretation | | | | | | | | ● | ● | ● | ● | ● | ● | ● | ● |
| Manuscript preparation and submission | ● | ● | ● | ● | ● | ● | ● | ● | ● | ● | ● | ● | ● | ● | ● |
| End of research project | | | | | | | | | | | | ● | ● | ● | |

BUDGET

| No. | Description | Unit price (RM) | Quantity | Price (RM) |
|-----|---|-----------------|----------|-----------------|
| 1 | RESEARCH MATERIALS & SUPPLIES | | | |
| 1.1 | Schlenker VAS Pain Scale Rulers 0-100mm with Slider | 40 | pcs | 4 160 00 |
| 1.2 | EMLA Cream 5%, 5G, 1s x 5 | 160 | Box | 12 1920 00 |
| 1.3 | Hansaplast Sensitive Kids Plaster 20's | 6 | box | 7 42 00 |
| | | | | |
| 2 | PROFESSIONAL SERVICE | | | |

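### The blinding stated in section 3.8 is delivered by the described procedures for A versus D only; nothing masks the 15-minute wait in C or the half amount of cream in B

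*Combined protocol and SAP*

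**What the plan says.** Section 3.1 describes a "single-blind, cross-over, randomized negative-controlled (without microneedle (MN)) trial". Section 3.8 goes further: "the study participants, outcome assessors, care providers and data handlers will be blinded to the study interventions", and "Only the statistician and the person who will be administering the interventions will be unblinded to the study interventions".

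The arms, defined under section 3.15, are "Intervention A: MN + 1 FTU EMLA 30 minutes application; Intervention B: MN + 0.5 FTU EMLA 30 minutes application"; C is microneedle with 1 FTU for 15 minutes; and D, the control, is 1 FTU for 30 minutes without microneedle.

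Section 3.9.2 describes one masking procedure. At a visit without microneedle, "an empty (i.e. without MN) PVA-containing PET sham patch will be applied instead". The masking argument added there concerns needle geometry and the pain or redness that needles might cause. The cream is applied as 1 or 0.5 FTU under an adhesive dressing. Then: "After the allocated application time (15 or 30 minutes), the attending medical officer will set up the transfusion line".

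Under section 3.9.3 the investigator records the child's VAS after the patch but before the cream, and again after cannulation. Section 3.8 also plans to ask blinded persons to guess the intervention and to compare the answers with chance. A blinding index is mentioned as something that could be computed.

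**The concern.** The arms differ in three features: microneedle, amount of cream and waiting time. The sham addresses the first only. The unqualified statement in section 3.8 therefore promises more than the procedures deliver, and it does not match the single-blind label in section 3.1.

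This matters because the primary endpoint is the child's own pain rating. Section 1.6 gives the research gap as whether microneedles allow less cream and faster action. Arms B and C answer those two questions, and their contrasts with control are the ones that no stated step fully masks. A child who expects more or less pain because of the length of the wait, or the amount of cream seen, may rate accordingly. The analysis cannot separate that from a treatment effect.

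**Working it through.** **Step 1: which contrasts the sham masks.** Arms are coded from section 3.15.

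| Arm | Microneedle | Cream (FTU) | Wait (min) |
|---|---|---|---|
| A | yes | 1 | 30 |
| B | yes | 0.5 | 30 |
| C | yes | 1 | 15 |
| D | no | 1 | 30 |

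| Pair | Features that differ | Differs only in what the sham hides? |
|---|---|---|
| A-D | microneedle | yes |
| A-B | amount | no |
| A-C | time | no |
| B-C | amount, time | no |
| B-D | microneedle, amount | no |
| C-D | microneedle, time | no |

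One of six pairs, and one of the three contrasts with control, is masked by design.

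**Step 2: which roles are affected.**
- *Child.* Experiences the whole wait and has up to four visits to compare. No step disguises the interval or the amount.
- *Investigator recording VAS.* Acts before the cream and after cannulation, so the interval between the two ratings is open to this person.
- *Cannulating medical officer.* Acts after the allocated time. A separate person applies patch and cream, and no text places the officer at application, so the officer's status is unclear.
- *Data handlers.* Section 3.8 provides coded sequences and gives the allocation only to the person administering it. Nothing shows that they are unmasked.

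**Step 3: what an expectation shift would do.** The plan gives no figure for this, so there is none to reproduce. Inputs are r = 0.7 and n = 23 (before attrition) or 26 (total), all from section 3.12. The shift is an assumption, expressed in SDs of a single VAS score, with that SD taken as equal across arms.

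SE of a pairwise contrast = √(2(1 − r)/n) SD:
- n = 23: √(0.6/23) = 0.162 SD
- n = 26: √(0.6/26) = 0.152 SD

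Noncentrality = shift/SE. The two-sided rejection rate at 0.05, with no true difference, comes from the noncentral t distribution. The range covers both n and error degrees of freedom from n − 1 to 3(n − 1).

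| Assumed shift (SD) | Shift/SE | Two-sided false-positive rate |
|---|---|---|
| 0 | 0 | 5% |
| 0.05 | 0.31 to 0.33 | about 6% |
| 0.10 | 0.62 to 0.66 | 9–10% |
| 0.15 | 0.93 to 0.99 | 14–16% |
| 0.25 | 1.55 to 1.65 | 32–37% |

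**The case against.** Several points on the other side are sound.

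- *Noticing is not knowing.* Section 3.9.2 says that in routine practice the wait is sometimes cut to 15 minutes, so a short wait need not tell a regular transfusion patient which arm applies. For B, the difference is about 0.369 against 0.68 g/cm² on a 1 cm × 1 cm grid under a dressing, at visits at least three weeks apart. A child may well miss it. A reader might infer that B and C are simply known to everyone; the documents do not show that. What stands is that no stated step prevents recognition, and that C is more exposed than B.
- *Not every role is affected.* A reader might infer that the blinding in section 3.8 fails for all four roles. The text does not support that for data handlers and leaves the cannulating officer open. Figure 5, the clinical flow, is not available here and may say who is present when.
- *The direction is unknown.* A shorter wait or less cream may lead a child to expect more pain, which would work against B and C. A child who infers that a microneedle was used may expect less. If the shift runs against C, the chance of a false result favouring C falls below its nominal 2.5%. The rates above therefore should not be read as a bias towards the time-saving claim.
- *Partly handled.* The guess questions are already planned, and skin conductance is a second outcome that is not self-reported, although anxiety may affect it. But the questions detect unmasking and do not prevent it. The index is optional, and no by-arm reporting or consequence is stated.

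**Conclusion.** The point holds in a limited form. The masking statement in section 3.8 is not delivered by the described procedures for five of six pairs, including B-D and C-D, and it conflicts with the single-blind label in section 3.1. The exposure is clearest for the wait in C, for the child and for the investigator recording VAS. It is weaker for the amount in B. A-D is masked by design, but success is not assured, since a child may feel the needles or see redness.

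The size depends on an assumed shift for which the documents give no value: from about 6% at 0.05 SD to 32–37% at 0.25 SD, with r = 0.7 and n = 23 to 26. It would be tempting to quote a false-positive chance of one third for C-D, but that is one point on a steep curve, and the sign of the shift is unknown. The supportable conclusion is that the reduced-amount and shorter-wait comparisons rest on a self-reported endpoint without full masking, and the plan should say so.

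**What to change.** 1. In sections 3.1 and 3.8, reconcile the blinding label and state by role and by contrast who is masked to what. Include whether the cannulating officer and the VAS recorder are kept unaware of amount and time, and how.
2. Describe A-D as masked by design, with success to be tested, and contrasts involving B or C as not masked for amount or time.
3. Commit to reporting the planned guess results and a blinding index by arm and role, beside each contrast.
4. Qualify the reduced-amount and shorter-wait conclusions accordingly, and limit the claim of a masked microneedle effect to A-D. The four-arm test is kept.

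The cost is revised wording and a by-arm summary of data already planned; no treatment or visit changes. The downside is a weaker claim for B and C.

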3.9 Clinical protocols

3.9.1 Fabrication of solid maltose microneedle

The MN array patch size is measured 1 cm x 1 cm, containing 36 microneedles with 1 mm needle gap in between. The maltose (Hayashibara, Okayama, Japan) MN dimension is designed to be around 400 μm in height, base width 100 μm , with a 3- μm tip radius. The standard deviation of needle heights within the patch is controlled to be less than 3%. The total patch thickness is therefore 0.8 mm. The MNs are grown on a soft cushion on top of Polyvinyl Alcohol (PVA) material (Kanto Chemical, Tokyo, Japan), with a Polyethylene Terephthalate (PET) patch (Acrysunday, Tokyo, Japan) to support the soft PVA patch as below. The base patch spans 125% larger than the array MN patch, with an estimated patch size of 1.5 cm x 1.5 cm. The overall size of the microneedle device is thus 1.7 cm (width) x 4 cm (length) x 0.5 cm (height). Figure 3 illustrates the schematic representation of microneedle prototypes that will be used in this study.

[figure not shown]

Figure 3. The schematic representation of microneedle prototypes.

Since the MN patch will be manually applied to the skin with a normal thumb force, various studies reported the hole diameter should be around $1/3$ of MN length.^{37,38} Therefore, this research's specification is speculated to achieve the desired penetration depth around 160 μm where the epidermal-dermal junction lies. To ensure a uniform force is applied all over the MN patch, the interventionist will stick a pillar handler of a size of 1 cm x 1cm x 4.9 cm on the bottom surface of MN patch with a double sellotape stuck onto it. The application of MN to the skin thus mimics a stamping action.

The maltose dissolving time is about 15s at a temperature between 25 and 30 °C and a humidity of more than 60%. Hence, in normal condition, the maltose MN is able to dissolve into the skin within 1 minute. For storage, the maltose MN is recommended to be stored at room temperature (upper limit not exceeding 40 °C) and at room humidity of less than 60% to avoid melting. The shelf time can last for more than 8 years, provided that the storage temperature is maintained at 25 °C and a room humidity of less than 10%.

3.9.2 Administration of interventions / controls

Prior to the administration of intervention / control, relevant clinic-demographic profiles (age, gender, ethnicity, anthropometric measurements, presence of comorbidities, thalassemia types etc) will be recorded and entered in the case report forms (CRFs) that are specifically designed for this study. This research study uses EMLA Cream (lidocaine 2.5% and prilocaine 2.5%) as the topical anaesthetic agent. EMLA Cream is a eutectic emulsion mixture of lidocaine and prilocaine at 1:1 ratio (i.e. each gram of EMLA cream contains lidocaine and prilocaine, 25 mg each). A eutectic mixture has a lower melting temperature than each constituent's melting temperature. The anaesthetic efficacy of EMLA cream will be assessed via pain induced by intravenous cannulation and the primary endpoint is the participant's VAS score measured after applying EMLA Cream (with and without MN application) for 15 and 30 minutes.

The window period given to EMLA Cream for its effect to work will be based on the usual clinical practice observation where it is usually applied for 30 minutes prior to intravenous catheterization. The rationale behind it is due to logistical issues and for the day care's operational convenience. Nevertheless, in a busy clinical setting, the application time is sometimes shortened to 15 minutes for slight anaesthetic effect. Thus, the study investigators postulate that, with the aid of microneedle, the time to onset of action for EMLA Cream could be greatly reduced, thus requiring less time to achieve its maximal effects.

According to the routine hospital protocol, all study participants received their blood transfusion based on the Good Clinical Practice (GCP) guidelines. For each participant, the individual will be randomized to one of the 24 treatment sequences (**Figure 4** and **Table 1**) and there will be a minimum of 3-weeks washout period before administering the next intervention. **Figure 5** illustrated the complete clinical flow for the first and subsequent visits, which includes the preliminary recruitment and randomization phases.

The investigator identified and drew a grid of 1cm × 1cm at the dorsum hand, which served as an ideal site for cannulation. The administrator of intervention (procedurist) will apply either 1 FTU of EMLA Cream (approximately 0.68 g/cm²) or 0.5 FTU (approximately 0.369 g/cm²) over the preparation area. If the patient is subjected to MN patching at his/her visit, the MN patch will be applied by thumb force and pressed firmly against the hand surface for 5 seconds to patch MN to the skin entirely before applying EMLA cream. Otherwise, an empty (i.e. without MN) PVA-containing PET sham patch will be applied instead. Besides, the height-to-base ratio (4:1) used for MN will also optimally minimise its adverse effects (pain, redness), thus preserving the masking (blinding) of study participants from knowing the types of interventions received. The preparation area will be covered with an adhesive dressing (Tegaderm™; 3M, Maplewood, Minnesota, USA) after EMLA cream application. After the allocated application time (15 or 30 minutes), the attending medical officer will set up the transfusion line with a 22-gauge hypodermic needle inserted into the dorsum hand. Throughout the process, the parents/guardians will be allowed to stay by the patient's side at all times.

3.9.3 Pain assessment

After a random treatment sequence was assigned to the study participants, the study participants will be guided on the operating manual for a 10-points, 100mm VAS pain score. The children will be presented with a ruler that contains 100-mm slots with “No Pain” written on the left side and “Worst Pain” on the opposite right side.

Before applying MN patch and EMLA Cream, the patients will be attached with the PainMonitor™ (Med-Storm Innovation AS, Oslo, Norway) device whereby the electrodes will be attached to the hypothenar eminence of the opposite hand not receiving the blood transfusion. The skin conductance peaks (in microSiemens (μ S) and the average rise time (in microSiemens per second (μ S/s)) will be recorded. Those parameters indicate the skin’s sympathetic nerve block induced by the applied EMLA cream.

After each procedure, the children then will be asked to move and place the slider in the slot that accurately describes his/her pain at the following time points: 1) 1 minute after application of MN/ sham patch and before EMLA Cream application (baseline VAS score); 2) 1 minute after IV cannulation. The investigator will record the location of the slot where the slider is placed in (millimetres (mm), clearly printed on the ruler’s backside) and this will be the participant’s VAS score. Throughout the process, there will be a trained nurse standing by at the day-care to assist the verification of the pain scale and to aid the participants who require additional assistance.

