3.13 Operational definitions of study variables

a) Independent variables

i) **Age:** The age of a study participant at the first study visit. The variable will be measured in years and month and modelled as a continuous numerical variable and will not be categorised into separate age groups.

ii) **Gender:** A categorical variable that will be recorded in the SPSS data frame as 0 = female (base category) and 1 = male. Missing data shall be recorded as 999

iii) **Ethnicity:** A categorical variable that will be recorded in the SPSS data frame as 0 = Malay (base category); 1 = Chinese; 2 = Indian; and 3 = Other ethnicity. Missing data shall be recorded as 999.

iv) **Body mass index (BMI):** A continuous numerical variable that is calculated using the standard body mass index formula; $BMI = \text{kg} / \text{m}^2$. This variable will be categorised according to Kuczmarski et al. (2000) classification⁵³:

<5% percentile = underweight (SPSS code: -1)

5% - <85% percentile = normal BMI (SPSS code: 0; base category)

85% - 95% percentile = Overweight (SPSS code: +1)

>95% percentile = Obese (SPSS code: +2)

The categorized variable will then be used as a predictor variable for statistical modelling purposes. Missing data will be recorded as 999 in the SPSS spreadsheet.

iv) **Intervention groups:** A categorical variable representing the types of interventions received by the study participants in each study visit. This variable will be recorded in the SPSS data frame as 0 = 1-FTU-EMLA only group (control, base category); 1 = MN + 0.5FTU EMLA (30 minutes), 2 = MN + 1FTU EMLA (15 minutes), 3 = MN + 1FTU EMLA (30 minutes).

v) **Baseline VAS score:** A continuous numerical variable that will be measured before the administration of intervention. This will be used as a predictor variable to control the confounding effect of heterogenous baseline VAS scores among study participants. Missing data will be recorded as 999 in the SPSS spreadsheet.

vi) **Baseline pain score obtained via PainMonitor™ device:** A continuous numerical variable that will be measured before the administration of intervention. This will be used as a predictor variable to control the confounding effect of heterogenous baseline VAS scores among study participants. Missing data will be recorded as 999 in the SPSS spreadsheet.

b) Dependent (outcome variables)

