3.14 Planned Statistical Analysis

The data will be initially checked and cross-examined with the information in the data collection sheet for accuracy, consistency and the amount of missing data. Missing data will be treated as Missing At Random (MAR) and multiple imputation will be considered to impute the missing values in order to reduce the biasness of the parameter estimates. Any variable with serious missing data problem (more than 40%) will be dropped from further analysis.^{54,55} All patients will be analysed according to the original randomization group, based on the intention-to-treat (ITT) analysis.

All data will be descriptively summarized as mean and standard deviation (SD) for the normally-distributed numerical variables (or median and interquartile range (IQR) for the non-normally distributed numerical variables) and frequency and percentage for categorical variable. For numerical data, the normality assumptions will be evaluated subjectively using the histogram with overlying normal distribution curve, box and whisker plot and steam-and-leaf diagrams and objectively using the Kolmogorov-Smirnov and Shapiro-Wilks tests ($p>0.05$ indicates normal distribution assumption is met). Fisher's coefficient of skewness will be subsequently utilized to assess the severity of skewness in non-normally distributed numerical variables using the following formula:

Fisher's coefficient of skewness: Skewness / standard error of skewness

Any value outside ± 2 range will indicate extreme skewness.⁵⁶

For the first and second objectives, repeated measure ANOVA and generalized mixed effect model (GLMM) with an identity link function will be used to assess and estimate the differences in terms of VAS score means between the periods of interventions, considering intra-subject correlations. For repeated measure ANOVA, Mauchly's test of sphericity will be used to assess the sphericity assumption. If sphericity assumption is violated, the Greenhouse-Geisser correction will be used if $\varepsilon < 0.75$ or the Huynh-Feldt correction if $\varepsilon > 0.75$.⁵⁷ Within-group analysis will be used to assess the significance of mean VAS score differences between treatment pairs. To assess the presence of carryover effect, the within group-between treatment sequence interaction effect will be assessed for statistical significance.

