For GLMM, the Restricted Maximum Likelihood (REML) estimator will be used to estimate the model parameters. The unadjusted and adjusted estimates of the parameters obtained using the GLMM will be examined, with and without the consideration of periodic effects. Random intercept model and robust variance estimators will be used for the calculation of standard errors. Likelihood ratio test will be utilized to compare the nested models and Akaike Information Criteria (AIC) and Bayesian Information Criteria will be used for comparing non-nested models. Multicollinearity between fixed effects (age, sex and treatment effects) will be evaluated using bivariate correlations. Besides, interaction effects (effect modification) between significant fixed predictors will also be assessed by evaluating the significance of interaction terms. Residual diagnostics will also be performed to ensure the validity of model assumptions and the presence of outliers and influential points will be investigated to ensure that they do not influence the model parameter estimates. The presence of any influential point will then be removed or corrected if these are due to measurement errors or wrong data entry or retained if the values are authentic. We will also carry out sensitivity analyses to investigate the effects of missing data under the Missing At Random (MAR) framework.

For the third and fourth objectives, the correlation between VAS pain score and PainMonitor™ device is tested using Pearson correlation coefficient if both VAS pain scores and PainMonitor™ device are normally distributed (Gaussian) and Spearman coefficient will be used if at least one pain scores (obtained by either measuring modality) are not normally distributed. Intraclass correlation coefficient (ICC) will be computed to assess the agreement between the VAS scores obtained using the two different modalities (VAS pain score vs PainMonitor™ device) and the results will be interpreted according to the Koo-Li criteria.⁵⁸ The Bland and Altman (B&A) plot will be obtained to further assess the agreement between the two scores. The limits of agreement obtained will be assessed to ensure there is an acceptable agreement between the pain measurement modalities.

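### The baseline VAS is taken after the randomised patch but is defined as pre-intervention and used as a predictor, so adjusting for it can bias the microneedle-versus-control contrast

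*Combined protocol and SAP*

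**What the plan says.** Section 3.9.3 lists two VAS readings per visit. The first is taken "1 minute after application of MN/ sham patch and before EMLA Cream application (baseline VAS score"; the second is taken 1 minute after cannulation. No VAS before the patch is listed.

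Section 3.13 describes the baseline VAS differently: "A continuous numerical variable that will be measured before the administration of intervention". It then gives the score a role in the models: "This will be used as a predictor variable to control the confounding effect of heterogenous baseline VAS scores among study participants".

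Section 3.14 plans several analyses of the cannulation VAS: "For the first and second objectives, repeated measure ANOVA and generalized mixed effect model (GLMM) with an identity link function will be used". For the GLMM, "The unadjusted and adjusted estimates of the parameters obtained using the GLMM will be examined". The only fixed effects it names appear in a collinearity check: "Multicollinearity between fixed effects (age, sex and treatment effects) will be evaluated using bivariate correlations". The baseline VAS is neither listed nor excluded there.

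On patch pain, section 3.9.2 says only that the needle geometry "will also optimally minimise its adverse effects (pain, redness), thus preserving the masking (blinding) of study participants".

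**The concern.** Sections 3.9.3 and 3.13 cannot both be followed. Staff working to 3.9.3 record a score after the patch. An analyst working to 3.13 treats that score as measured before any intervention and adjusts for it.

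The patch is the component under test. Arms A, B and C receive the microneedle and arm D receives the sham, and the general objective in 2.1 compares pain with and without the microneedle. Pain felt 1 minute after the patch may therefore be an effect of treatment. A model that holds it fixed asks how cannulation pain would compare between microneedle and control visits at which the patch hurt equally. That is not the question in objective 2.2.1.

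At stake is the microneedle-versus-control contrast in the adjusted GLMM. If the microneedle stings more than the sham, adjustment credits it with a benefit it did not produce. If it stings less, adjustment hides benefit.

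**Working it through.** **Which reading is possible.** Could *intervention* in 3.13 mean EMLA alone, so that the two sections agree? No. The same section codes the intervention variable as EMLA only (0) against three microneedle-plus-EMLA regimens (1 to 3), so the microneedle is part of the intervention. The bias would in any case arise whatever the score is called.

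**Is the adjustment needed?** The reason given in 3.13 is heterogeneity among participants. Each child receives all four interventions, so the crossover already removes differences between children from the treatment contrasts.

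**Formula.** Let δ be the microneedle-minus-sham difference in the post-patch VAS, β the fitted slope of cannulation VAS on post-patch VAS, and τ the true microneedle-minus-control effect. Then

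adjusted contrast ≈ τ − β × δ, so bias ≈ −β × δ.

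The bias is zero if δ = 0 or β = 0. A score taken before the patch has δ = 0 by design.

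**Inputs from the plan (3.12).** n = 23 before drop-out, 4 measurements, r = 0.7. The 23 can be reproduced with f = d/2 = 0.4 and ε = 0.75: λ = 0.4² × 23 × 4 × 0.75 = 11.04, power 0.815. With 10% drop-out, 23/0.9 = 25.6, rounded up to 26. The plan gives no figure for patch pain, VAS SD or the correlation between the two scores.

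**Assumed inputs.** SD 20 mm for both scores, and r = 0.7 applied to both. This gives a between-child variance of 0.7 × 400 = 280 and a within-child variance of 0.3 × 400 = 120. True effect zero, patch pain additive, no truncation at 0 or 100. The link between the two scores is 0.3, 0.5 or 0.7, either through the child only or through both child and visit.

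**Check.** Random-intercept REML with three treatment indicators plus the post-patch VAS, 800 to 1,500 simulated trials per setting, Monte Carlo SE 0.05 to 0.12 mm. Mean adjusted microneedle-minus-control difference (mm) at link 0.3 / 0.5 / 0.7:

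| Excess patch pain δ | Child-level link only | Child- and visit-level link |
|---|---|---|
| 0 mm | within 0.06 of 0 | within 0.06 of 0 |
| 5 mm | -0.3 / -0.6 / -1.0 | -1.7 / -2.5 / -3.5 |
| 10 mm | -0.7 / -1.2 / -1.8 | -3.0 / -5.0 / -7.0 |
| 15 mm | -1.1 / -2.0 / -3.0 | -4.5 / -7.5 / -10.4 |
| -10 mm | +0.7 / +1.3 / +2.0 | +3.0 / +5.1 / +7.0 |

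The formula agrees. With both links the fitted slope is 0.30 to 0.70, and 0.70 × 10 = 7.0. With the child-level link only, the slope is 0.07 to 0.19, because a random-intercept model with an uncentred covariate mixes between-child and within-child information.

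Rejection of A versus D at δ = 10 mm is 6.4 / 6.9 / 8.9% (child only) and 15.1 / 38.8 / 80.0% (both levels), against 4.5 to 5.5% unadjusted. The adjusted A-minus-B difference stayed within 0.19 mm of zero, and unadjusted means within 0.23 mm of zero.

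**Second check.** A within-child regression with n = 26, a true effect of -10 mm and δ = 10 mm gave -11.9 / -15.1 / -18.0 mm at β = 0.2 / 0.5 / 0.8. The unadjusted estimate stayed near -10. The bias is again −β × δ and does not depend on the true effect.

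**The case against.** The strongest reply is that little depends on this model. The trial is sized on RM-ANOVA, 3.14 names RM-ANOVA first, and no covariate is attached to it. An unadjusted GLMM is also planned. The three microneedle arms share the same patch, so contrasts among them are largely spared. The only fixed effects that 3.14 names are age, sex and treatment, so use of the post-patch VAS rests on 3.13 alone. All of this is right and limits the exposure. It does not remove it: 3.13 states outright that the score will be a predictor, and the bracket in 3.14 describes a collinearity check, not the model.

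A second reply is that the figures are not anchored. That also stands. The 80% rejection rate needs 10 mm excess patch pain and a 0.7 link at both levels, whereas 3.9.2 expects little microneedle pain. Clipping scores to 0–100, with assumed latent means of 0 for the sham patch and 40 for cannulation, cuts the realised excess from 10 to 6 mm, the largest bias from -7.0 to -4.7 mm, and that rejection rate to about 44%. The equal-SD assumption errs the other way: with a patch-score SD of 10 mm the slope becomes 0.7 × 20/10 = 1.4 and the bias -14.0 mm. The plan's robust standard errors barely change the top rejection rate (80.8% against 80.2%). The table illustrates the mechanism and does not bound the bias.

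Third, the per-visit flow in Figure 5 is not shown in the text reviewed, so the absence of a pre-patch VAS rests on the list in 3.9.3. That list is explicit.

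**Conclusion.** The concern holds. The contradiction between 3.9.3 and 3.13 is in the text, and confidence in it is high. As written, the adjusted GLMM would condition on a score measured after the randomised patch, and its microneedle-versus-control estimate can be biased by about −β × δ. Confidence in direction and size is low, because patch pain, SD and the correlation between the scores are all assumptions. For 10 mm excess patch pain the illustrative bias runs from under 1 mm to 7 mm in favour of the microneedle. It is nil at zero excess and has the opposite sign if the microneedle hurts less than the sham. The RM-ANOVA and the unadjusted GLMM are unaffected, contrasts among A, B and C are largely so, and the sample size does not change. It should be corrected before analysis because the adjustment is not needed in this design and removing it is free.

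**What to change.** Reconcile 3.9.3 and 3.13.

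- **Default:** delete the post-patch VAS from the predictors in 3.13. This costs wording only.
- **Alternative:** if a baseline covariate is wanted, add one slider reading per visit before the patch and use only that. A suitable moment already exists: "Before applying MN patch and EMLA Cream, the patients will be attached with the PainMonitor" device. This costs one slider placement per visit. The score may sit near zero because nothing painful has yet happened, so its value as a covariate is not assured. The choice should be made early, because a missed pre-patch reading cannot be recovered.
- **In either case:** rename the 1-minute score the patch-pain score, report it as a separate outcome (microneedle versus sham), and keep it out of every model that estimates the treatment effect on cannulation VAS.
- **In 3.14:** list the covariates of the adjusted GLMM.

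A related gap can be closed in the same edit. Section 3.14 lists RM-ANOVA, unadjusted GLMM and adjusted GLMM without saying which decides objective 2.2.1, so there is no rule if they disagree. Naming one costs a sentence. The case for removing the covariate does not depend on it.
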